10.1 Subject Completion

Subjects completing all 11 study visits (including the 5 phone visits) will be considered to have completed study.

10.2 Subject Compensation

Subjects will be paid \$50 for the completion of each of the 6 in-clinic visits, up to \$300 for the entire study.

10.3 Subject Withdrawal

Subject may withdraw from study at any time for any reason without penalty or be terminated from the study by the clinical investigator (see provisions for termination by study team.) Investigational team will document the reason(s) for withdrawal. In the event a subject chooses to withdraw from study before Visit 3, the safety procedures described in Section 7.3 will be performed ideally within 3 days following subject’s decision to withdraw. For all subjects who

withdraw, all final safety assessments will be collected regardless of time elapsed since previous visit. In addition to the termination visit, subjects who withdraw early will be contacted within 7 days by study staff via telephone to assess development of new and/or ongoing AEs and concomitant medications.

Subject's participation may be terminated at the discretion of the investigator. Individuals may be withdrawn for the following reasons:

- Clinically significant adverse events
- Lost to follow-up
- Protocol violations
- Inability to tolerate study medication
- Other

11 Adverse Events (AE) and Serious Adverse Events (SAE)

11.1 Definition of AE

An adverse event is any symptom, sign, illness or experience which develops or worsens in severity during the course of the study. Intercurrent illnesses or injuries should be regarded as adverse events. Abnormal results of diagnostic procedures are considered to be adverse events if the abnormality:

- Results in study withdrawal
- Is associated with clinical signs or symptoms
- Leads to treatment or to further diagnostic tests
- Is considered by the investigator to be of clinical significance

11.2 Definition of SAE

Adverse events are classified as either serious or non-serious. A serious adverse event is any event that results in:

- Severe hypoglycemia
- Severe hyperglycemia
- Diabetic ketoacidosis
- Death
- Life-threatening situation
- Hospitalization or prolongation of hospitalization
- Disability or incapacitation
- Congenital abnormality or birth defect
- Other events determined by investigator to be medically significant in which subject's well-being is jeopardized

11.3 Relationship of Adverse Event to Study Treatment

The study investigator will assess the relationship of any adverse event to be related or unrelated by determining if there is a reasonable possibility that the adverse event may have been caused by the study treatment.

To ensure consistency of adverse event causality assessments, investigators should apply the following general guideline when determining whether an adverse event is related:

- **Unrelated:** The AE is clearly not related to a study drug/device and a likely alternative etiology exists such as an underlying disease, environmental or toxic factors or other therapy.
- **Unlikely Related:** The AE does not follow a reasonable temporal sequence during or after use of study drug/device and a more likely alternative etiology exists such as an underlying disease, environmental or toxic factors, or other therapy.
- **Possibly Related:** The AE occurred in a reasonable time during or after use of study drug/device; but could be related to another factor such as an underlying disease, environmental or toxic factors, or other therapy; and there is a possible, though weak, scientific basis for establishing a causal association between the AE and the study drug/device.

- **Probably Related:** The AE occurred in a reasonable time during or after use of study drug/device; is unlikely to be related to another factor such as an underlying disease, environmental or toxic factors, or other therapy; and there is a plausible, though not strong, scientific basis for establishing a causal association between the AE and the study drug/device.
- **Definitely Related:** The AE occurred in a reasonable time during or after use of study drug/device; cannot be explained by another factor such as an underlying disease, environmental or toxic factors, or therapy; and there is a strong scientific basis for establishing a causal association between the AE and the study drug/device.
- **Not Assessable:** Causality of an adverse event cannot be judged because information is insufficient or contradictory, and which cannot be supplemented or verified.

11.4 Intensity of Adverse Event

The intensity of an adverse event will be rated as (1) mild, (2) moderate, or (3) severe. The term “severe” is a measure of intensity; thus a severe adverse event is not necessarily serious. For example, itching for several days may be rated as severe, but may not be clinically serious.

- **MILD:** Usually transient, requires no special treatment, and does not interfere with the participant’s daily activities.
- **MODERATE:** Usually causes a low level of inconvenience or concern to the participant and may interfere with daily activities, but is usually ameliorated by simple therapeutic measures.
- **SEVERE:** Interrupts a participant’s usual daily activities and generally requires systemic drug therapy or other treatment.

11.5 Timing of Event Detection and Reporting

Upon consenting, a subject is considered to be a subject in the study, and until that person either withdraws or completes study, AEs and SAEs will be recorded. The investigational team will promptly report any AE/SAE as required per federal guidelines. Each principal investigator is responsible for reporting serious study-related adverse events and abiding by any other reporting requirements specific to his/her Institutional Review Board or Ethics Committee.

11.6 Glycemic Events

11.6.1 Hypoglycemic Events

Hypoglycemia not associated with an Adverse Device Effect is only reportable as a serious adverse event (SAE) when the following definition for severe hypoglycemia is met: the event required assistance of another person due to altered consciousness, and required another person to actively administer carbohydrate, glucagon, or other resuscitative actions. This means that the participant was impaired cognitively to the point that he/she was unable to treat himself/herself, was unable to verbalize his/her needs, was incoherent, disoriented, and/or combative, or experienced seizure or loss of consciousness. These episodes may be associated with sufficient neuroglycopenia to induce seizure or loss of consciousness. If plasma glucose measurements are not available during such an event, neurological recovery attributable to the restoration of plasma glucose to normal is considered sufficient evidence that the event was induced by a low plasma glucose concentration. Non-severe hypoglycemia will not be reported as an AE (but will be captured by the data analysis).

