Intranasal (IN)	A method of drug delivery that is particularly applicable to delivering centrally acting medications into the central nervous system.
Investigator Brochure (IB)	A comprehensive document summarizing the body of information about an investigational product
Michigan Neuropathy Screening Instrument (MNSI)	A standardized physical exam technique using light touch, vibratory sensation and ankle reflexes to establish risk for peripheral neuropathy
Repeated Battery for the Assessment of Neuropsychological Status (RBANS)	A standardized neuropsychological assessment with five scores for each of five domains (immediate memory, visuospatial/constructional, language, attention, and delayed memory).
Serious adverse events (SAE)	Any symptom, sign, illness or experience that develops during the study and results in a life-threatening situation, hospitalization, significant disability, and other events determined by the investigator to be significant.
Trail Making Test (TMT) Parts A & B	A standardized neuropsychological test of visual attention and task switching.

Protocol Summary

PROTOCOL TITLE	Intranasal Insulin: A Novel Therapy for Hypoglycemia Unawareness in Type 1 Diabetes
SHORT TITLE	IN Insulin in Type 1 Diabetes (T1D) Hypoglycemia Unawareness: Safety Only Phase
STUDY PHASE	Phase II
STUDY OBJECTIVES AND PURPOSE	

Primary Objective: Demonstrate no significant increase in dangerous hypoglycemia with administration of intranasal insulin in T1D participants with intact awareness of hypoglycemia
	

Secondary Objectives:
 
 1. Describe changes in overall glycemic control with administration of intranasal insulin in T1D participants with intact awareness of hypoglycemia 2. Describe changes in hypoglycemia awareness with administration of intranasal insulin in T1D participants with intact awareness of hypoglycemia 3. Describe changes in safety endpoints with administration of intranasal insulin in T1D participants with intact awareness of hypoglycemia 	

Exploratory Objective: Describe changes in memory, attention and executive function with administration of intranasal insulin in T1D participants with intact awareness of hypoglycemia
	
STUDY DESIGN	
Study Type	Safety
Control Type	Placebo Crossover
Study Indication Type	Treatment
Randomization Schema	Insulin vs Placebo First
Device	SipNose intranasal device

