11.6.2 Hyperglycemic/Ketotic Events

Hyperglycemia/ketotic events not associated with an Adverse Device Effect is only reportable as a serious adverse event (SAE) when either of the following criteria are met:

1. Severe hyperglycemia:
 - Blood glucose >300 mg/dL, urine ketones moderate or large (or blood ketone >1.5 mmol/L), or accompanied by symptoms of nausea, vomiting or abdominal pain
2. Hyperglycemic events are additionally classified as DKA if all of the following are present:
 - Blood glucose >250 mg/dL

- Symptoms such as polyuria, polydipsia, nausea, vomiting or abdominal pain
- Serum ketones >1.5 mmol/L or large/moderate urine ketones
- Either arterial blood pH <7.30 or venous pH <7.24, or serum bicarbonate <15 mEq/L
- Treatment provided in a health care facility

Non-severe hyperglycemia will not be reported as an AE as mild hyperglycemia is an expected occurrence in the study population.

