13.2 Data Safety Monitoring Board

The DSMB will be an independent group who are not participating in the trial and have no direct affiliation with HealthPartners Center for Memory and Aging or IDC. They will serve as an advisory panel to HealthPartners Center for Memory and Aging/IDC. The DSMB will be comprised of three appropriately qualified individuals. The DSMB Charter will be established prior to initiation of the study. The DSMB responsibilities include but are not limited to the following:

- Monitoring the study for compliance to the protocol.
- Stopping the study if the rate of SAE's raises safety concerns. The details will be specified in the DSMB charter.

The DSMB will convene following the study completion of the 10 subjects in phase 1, or earlier in the case of SAEs. During the course of the trial, the DSMB will review accumulating safety data to monitor for incidence of trends that would warrant termination of the trial. The frequency of the DSMB meetings, responsibilities, membership, and procedures will be documented in the DSMB charter.

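### Sections 11.2 and 11.6 contradict each other on glycemic hospital admissions, so an admission outside the 11.6 severe definitions can be missing from both the SAE and the AE counts

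*Combined protocol and SAP*

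**What the plan says.** Section 11.2 lists the outcomes that make an event serious. One is "Hospitalization or prolongation of hospitalization", with no exception for glycemic events. Severe hypoglycemia, severe hyperglycemia and DKA are separate items on the same list, so hospitalization counts in its own right. The Definitions table agrees: an SAE is something that "results in a life-threatening situation, hospitalization, significant disability", among other outcomes.

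Section 11.6.1 sets a narrower rule. Where the device is not implicated, a hypoglycemic event "is only reportable as a serious adverse event (SAE) when the following definition for severe hypoglycemia is met". What must be met is then spelled out as follows: "the event required assistance of another person due to altered consciousness, and required another person to actively administer carbohydrate, glucagon, or other resuscitative actions". The section ends: "Non-severe hypoglycemia will not be reported as an AE (but will be captured by the data analysis").

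Section 11.6.2 is built the same way. A hyperglycemic or ketotic event without an Adverse Device Effect "is only reportable as a serious adverse event (SAE) when either of the following criteria are met", the two criteria being severe hyperglycemia and DKA. Non-severe hyperglycemia is also kept off the AE record.

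Section 13.2 has the DSMB convene after the 10 subjects complete, or sooner if SAEs occur, and gives as one of its duties "Stopping the study if the rate of SAE's raises safety concerns". Section 4.2 lists adverse events among the secondary safety outcomes.

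**The concern.** The primary objective is to show that intranasal insulin does not increase dangerous hypoglycemia in people with type 1 diabetes. For the events closest to that objective, two sections of the protocol give opposite answers on whether a hospital admission is serious. A coordinator who completes forms from 11.6 and one who completes them from 11.2 would produce different SAE listings from the same facts, and each could point to the protocol.

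At stake is what the DSMB sees and what the final safety table shows. A glycemic admission classified under 11.6 would not bring the DSMB together early, would not enter the SAE rate, and would not appear in the adverse event summary.

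**Working it through.** The plan gives no figure on this point, and the sample size and power in Section 12.4 are not affected. The check applies both rules to the same cases.

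**Step 1. Apply each rule.** The cases are hypothetical, with no Adverse Device Effect.

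| Case | Under 11.2 | SAE under 11.6? | AE under 11.6? |
|---|---|---|---|
| A. Conscious participant self-treats and is admitted for recurrent lows | SAE (hospitalization) | No | No |
| B. Admitted at 280 mg/dL with small urine ketones, blood ketone not above 1.5 mmol/L, no nausea, vomiting or abdominal pain | SAE (hospitalization) | No | No |
| C. Disoriented participant has to be treated by another person and is admitted | SAE | Yes | Already counted as an SAE |
| D. Withdraws because of repeated self-treated lows, not admitted | Not an SAE by hospitalization | No | No |

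Case A fails the 11.6.1 definition because that definition needs both altered consciousness and active treatment by someone else. Carbohydrate given by hospital staff would not change this, since the altered-consciousness part is still not met. The event is then non-severe, and so excluded as an AE.

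Case B fails both 11.6.2 criteria. The severe hyperglycemia item can be read as three alternatives (glucose above 300 mg/dL, ketones, symptoms), or as the glucose threshold plus one of the other two. At 280 mg/dL, with ketones below the stated levels and none of the listed symptoms, it fails either way. DKA requires every listed element, and the ketone element is missing.

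Case C is an SAE under both sections. The contradiction is therefore confined to admissions like A and B.

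**Step 2. Look for text that settles the order.**
- Section 11.5 requires prompt reporting under federal guidelines, but does not say whether 11.2 or 11.6 decides what counts as an SAE.
- Section 11.7 leaves disease-related abnormal findings out unless the investigator judges them more severe than expected. That is discretion, not a rule of precedence.
- The data analysis that 11.6.1 relies on is the CGM summary. Percent time below 54 mg/dL records glucose values, not an admission or a reason for leaving.
- For case D, Section 10.3 has the team document the reason for withdrawal, but not as an AE. Section 12.1 excludes subjects with missing data, so a participant who leaves and has missing CGM data could also drop out of the analysis.

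Nothing in the documents resolves the conflict.

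**Step 3. Size.** With 10 completers, one case like A moves the observed SAE proportion from 0/10 to 1/10. It also changes whether the one early-meeting trigger named in 13.2 has been met. No admission rate is given, so an expected number of such events cannot be calculated.

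**The case against.** The strongest reply is that a competent site would report the admission anyway. Hospitalization is on the 11.2 list, the investigator may call any event medically significant under the same list, and 11.5 points to federal guidelines. This is a fair account of what may well happen. It shows that the event need not be lost, but not that the protocol gives one answer.

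The second reply is that keeping lows off the AE forms is deliberate and sensible. Section 1.1 puts mild hypoglycemia at 1 to 2 events per patient per week, and CGM measures it better than a form would. That stands, and the fix leaves it alone.

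The third is that other records exist: reasons for withdrawal, final safety assessments and a call within 7 days under 10.3, and staff review of CGM data at the phone visits. That also stands. A withdrawal because of lows is on file. It is just not in the adverse event data.

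A reader might also cite "Results in study withdrawal" in Section 11.1 as proof that a withdrawal because of lows must already be an AE. It is not: that item qualifies abnormal results of diagnostic procedures and is not a general rule about withdrawal.

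**Conclusion.** The contradiction is real and unresolved, and it is limited to glycemic admissions (or events meeting another 11.2 criterion) that fall outside the 11.6 severe definitions. For these, following 11.6 literally leaves both the SAE and the AE counts without the event. The conclusion rests on the wording alone and assumes no particular event rate. It does not touch the primary estimate.

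Four stronger readings are tempting and are not supported:
- **That 11.6 overrides 11.2.** There is no precedence clause. The two sections conflict.
- **That SAEs are the only basis for stopping.** Section 13.2 also has the DSMB review accumulating safety data for trends that would warrant termination, and leaves procedures to a charter that is not supplied. SAEs are only the one early-meeting trigger that the protocol names.
- **That everything short of coma is lost.** The severe definition extends to participants who are incoherent, disoriented, combative or unable to treat themselves, when another person treats them.
- **That the Adverse Device Effect exception should be widened to the study drug.** That qualifier governs only the SAE sentence, so changing it would not restore AE reporting of non-severe lows. If it did work that way, routine lows could flood the forms: 10 subjects × 17/7 weeks × 1 to 2 per week gives about 24 to 49 in the insulin period. Relatedness could be judged with treatment known, because Sections 7.1.2 and 7.1.7 require the 4-hour observation only for those starting insulin.

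**What to change.** Reconcile the sections by adding one sentence to both 11.6.1 and 11.6.2:

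> These limits do not apply to a glycemic event that meets any other criterion in Section 11.2 (e.g. hospitalization), which is reported as an SAE, or that leads to withdrawal from the study, which is recorded at least as an AE.

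Leave routine self-treated lows outside AE reporting, and leave the Adverse Device Effect wording as it stands. The change is to protocol text only, with no new visits or procedures. The downside is a few more AE and SAE forms.

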11.6.2 Hyperglycemic/Ketotic Events

Hyperglycemia/ketotic events not associated with an Adverse Device Effect is only reportable as a serious adverse event (SAE) when either of the following criteria are met:

1. Severe hyperglycemia:
 - Blood glucose >300 mg/dL, urine ketones moderate or large (or blood ketone >1.5 mmol/L), or accompanied by symptoms of nausea, vomiting or abdominal pain
2. Hyperglycemic events are additionally classified as DKA if all of the following are present:
 - Blood glucose >250 mg/dL

- Symptoms such as polyuria, polydipsia, nausea, vomiting or abdominal pain
- Serum ketones >1.5 mmol/L or large/moderate urine ketones
- Either arterial blood pH <7.30 or venous pH <7.24, or serum bicarbonate <15 mEq/L
- Treatment provided in a health care facility

Non-severe hyperglycemia will not be reported as an AE as mild hyperglycemia is an expected occurrence in the study population.

11.7 Clinical Laboratory Abnormalities & Other Abnormal Assessments as AEs & SAEs

Any new abnormal vital sign, examination, or laboratory finding judged clinically significant by the investigator will be documented as an AE or SAE, if meeting the definitions for such. Abnormal lab findings or other abnormal assessments associated with the disease under study will not be considered AEs or SAEs unless more severe than expected, as judged by the investigator.

11.8 SipNose Failures and Malfunctions

All failures and malfunctions of the device will be recorded. All performance issues and malfunctions will be reported to SipNose during the study and in the clinical results (e.g., final report).

11.9 Pregnancy Reporting

If pregnancy occurs, the participant will be discontinued from the study. Urine pregnancy test may be done at any time if pregnancy is suspected. The occurrence of pregnancy will be reported on an AE Form.

12 Data Analysis and Statistical Considerations

12.1 Analysis Overview

Discrete variables will be summarized using frequencies and percentages, while continuous variables will be summarized by mean and standard deviation or median and interquartile range, as appropriate. Baseline variables will be compared between groups to ensure randomization achieved a balanced design. Distribution of the outcome variables will be assessed to determine if the planned analyses are appropriate. All analyses will be performed on an intention-to-treat basis. Missing data will be considered to be missing at random and those subjects will be excluded from analysis. If a large proportion of data is missing (>10%), we will compare baseline characteristics between subjects with missing and non-missing data. No adjustment for multiple comparisons will be done. All statistical analyses will be performed in SAS Version 9.4.

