Study Design	Prospective, randomized, cross-over, placebo controlled
Planned Duration of Subject Participation	10 weeks
Planned Duration of Treatment with IN insulin	14-20 days
PRIMARY ENDPOINTS	
Dangerous hypoglycemia defined by percent time below range (<54 mg/dL), from real-time continuous glucose monitoring (CGM)	
SECONDARY ENDPOINTS	

 1. Overall metrics and glycemic control from real-time CGM data during each treatment period defined as: 
 a. Percent time in range (70-180 mg/dL) b. Percent time below range (<70 mg/dL) 	

- c. Percent time above range (>180 mg/dL, >250 mg/dL)
 - d. Mean glucose
 - e. Coefficient of variation (%CV)
 - f. Glucose management indicator (GMI)
 - g. Percent time of active sensor wear
2. Hypoglycemia awareness measured three ways using:
 - a. 3 hypoglycemia unawareness questionnaires/scores (Gold Score, Clarke survey, HypoA-Q)
 - b. Time from CGM reading of, <70 mg/dL, 54-<70 mg/dL and <54 mg/dL to time of participant hypoglycemia awareness obtained from participant journals
 - c. Glucose value from real-time CGM at onset time of hypoglycemia awareness obtained from participant journals
 3. Safety outcomes include:
 - a. Adverse events
 - b. Neuropathy test changes
 - c. Review of patient non-study medications
 - d. HbA1c
 - e. EKG
 - f. Smell test changes
 - g. C-SSRS assessment

EXPLORATORY ENDPOINTS

1. Memory and attention using Repeatable Battery for the Assessment of Neuropsychological Status (RBANS)
2. Executive function using Trail Making Parts A and B

INVESTIGATIONAL PRODUCTS, DOSE AND MODE OF ADMINISTRATION

Investigational Product	Humulin-R 20 IU/IN (0.1ml/10 units IN in each nostril) BID
-------------------------	--

SUBJECT SELECTION

Targeted Accrual	10 subjects are anticipated to complete this study. We estimate a need to consent up to 20 subjects in order to reach this goal.
------------------	--

INCLUSION CRITERIA

- Adult patients (age ≥18) with type 1 diabetes diagnosis and a duration of diabetes of at least 10 years
- Gold score <4
- HbA1c ≥6.5% within the last 3 months or at screen visit
- Stable insulin regimen (MDI or insulin pump) for at least 3 months, as deemed stable by principal investigator
- Depression/anxiety medications stable for at least 3 months
- Ability and willingness to wear CGM continuously during study participation

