4.3 Exploratory Endpoints

- Memory and attention using Repeatable Battery for the Assessment of Neuropsychological Status (RBANS)
- Executive function using Trail Making Parts A and B

5 Study Design

This study is a single center trial designed to assess the safety of administering intranasal (IN) regular insulin in subjects with type 1 diabetes and intact hypoglycemia awareness Figure 4.

After written informed consent has been obtained, subjects will be screened to assess study eligibility based on study inclusion/exclusion criteria. Subjects who are eligible at the end of the screening visit (Visit 1) will be scheduled for a baseline visit to take place 1 to 2 weeks later (Visit 2). During the baseline/randomization visit, subjects will be administered the hypoglycemia and cognitive questionnaires and tests. Patients then are randomized 1:1 to either treatment with intranasal insulin or placebo. They will wear two 10-day real-time CGMs, and then crossover to the other group for another two 10-day period following a 2 week washout period. A final safety/assessment visit will take place up to 1 week after visit 10.

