7.1.5 Visit 5: End of Treatment Period 1 (Day 17 +/- 3 days)

The following procedures will be performed at this visit:

- Safety check and assess AEs/SAEs
- Gold score (for data collection purposes only)
- Medication review for any changes since screening
- VS (blood pressure/pulse)
- MNSI survey
- Hypo surveys
- Document BG values before and after cognitive testing
- Cognitive tests (study drug must have been taken prior to testing)
- Review daily diary
- Evaluate CGM for adequate data collected
- Inventory returned devices
- Download SMBG for safety, if used
- Download and review CGM data
- Provider to see patient at this visit for visit assessment review
- In the event the study site is recommending no non-essential in person clinic contacts (such as during the COVID-19 pandemic), this visit may be done remotely and study staff will obtain as much of the above procedural information as possible. Procedures such as MNSI survey and VS may not be able to be done.

7.1.6 Phone Visit 6: Safety Check 1 Week into the 2 Week Washout (Day 24 +/-2 days)

The following procedures will be performed at this visit:

- Study staff phone call to assess for AEs/SEs

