12.3 Statistical Analysis of Secondary and Exploratory Outcomes

The secondary and exploratory objectives are purely descriptive. No inferential statistics will be performed. All measures of overall glycemic control, hypoglycemia awareness, and safety endpoints will be reported using the appropriate summary statistics. Values will be reported from baseline and conclusion of each dosing period.

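### Section 12.1 sets no separate rule for adverse events, so either of its two sentences, intention-to-treat or exclusion for missing data, can understate adverse events on insulin in this crossover

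*Combined protocol and SAP*

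**What the plan says.** Section 12.1 (Analysis Overview) sets one basis for everything: "All analyses will be performed on an intention-to-treat basis". Its next sentence reads: "Missing data will be considered to be missing at random and those subjects will be excluded from analysis". Neither carries an exception for safety data.

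Adverse events are a listed secondary safety outcome (Section 4.2 and the Protocol Summary), so both sentences reach them. Section 12.3 adds only that "All measures of overall glycemic control, hypoglycemia awareness, and safety endpoints will be reported using the appropriate summary statistics" and that "No inferential statistics will be performed". Its one timing rule, values at baseline and at the end of each dosing period, suits measurements but not events. No section defines a safety population, names a denominator for an adverse event table, or says whether an event belongs to insulin, placebo, washout or follow-up.

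The design is a two-period crossover: "Patients then are randomized 1:1 to either treatment with intranasal insulin or placebo" (Section 5), after which each participant switches. On collection, Section 11.5 says that "until that person either withdraws or completes study, AEs and SAEs will be recorded". This includes the washout call (Section 7.1.6: "Study staff phone call to assess for AEs/SEs") and the final safety visit (Section 7.1.11).

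**The concern.** In a parallel-group trial, intention-to-treat and as-treated safety counts usually differ by a few people. In a crossover the difference is structural: everyone is assigned to both treatments, so counting by assignment puts everyone in both denominators, including people who never took one of the products.

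The protocol shows how this could happen. A placebo-first participant can leave before Visit 7. Section 7.1.7 also lets a saline start go ahead remotely when clinic contact is restricted, but postpones an insulin start by lengthening the washout. That delay falls only on placebo-first participants. It is not itself a loss, but it lengthens the time in which one can occur.

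The other sentence in Section 12.1 creates a different problem. It removes subjects, not periods. An insulin-first participant withdrawn for a clinically significant adverse event, which Section 10.3 lists as a reason for withdrawal, has no second-period data and could be dropped with the event that caused the withdrawal.

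The short title describes a safety-only phase. Because adverse events are reported descriptively, the raw percentages are the result. With about 10 participants, moving one person changes them visibly.

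**Working it through.** **Is there a stated figure to reproduce?** Not for this point. The documents give no adverse event rate, no number randomised and no dropout rate after randomisation. The power figure in Section 12.4 does reproduce: SE = 1.4 × √(2/10) = 0.626, noncentrality = 2/0.626 = 3.19, 8 degrees of freedom and one-sided 0.025 give 79.84% against the stated 79.8%. It concerns the CGM endpoint and this point does not affect it.

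**Inputs.** From the documents: 10 expected completers and up to 20 consented (Protocol Summary), and 1:1 allocation (Section 5). Assumed: R randomised, d of them never exposed to insulin, and x = 3 exposed participants with an event on insulin.

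**Intention-to-treat reading.** The rate by treatment received is x/(R−d). The rate by assignment is x/R. Their ratio is (R−d)/R.

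| R | d | by assignment | by treatment received | ratio |
|---|---|---|---|---|
| 12 | 0 | 3/12 = 25.0% | 3/12 = 25.0% | 1.00 |
| 12 | 1 | 3/12 = 25.0% | 3/11 = 27.3% | 0.92 |
| 12 | 2 | 3/12 = 25.0% | 3/10 = 30.0% | 0.83 |
| 12 | 3 | 3/12 = 25.0% | 3/9 = 33.3% | 0.75 |
| 20 | 5 | 3/20 = 15.0% | 3/15 = 20.0% | 0.75 |

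Under 1:1 allocation, d = 2 of 12 means two of about six placebo-first participants, and d = 5 of 20 means five of about ten.

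**No events seen.** The one-sided 95% upper bound is 1 − 0.05^(1/n): 22.1% for n = 12 and 25.9% for n = 10. Section 12.3 plans no such bound, but a reader of the table could draw one.

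**Exclusion reading.** Take R = 12 and d = 2, so 10 are exposed to insulin. Suppose one of the three with an event is an insulin-first participant who withdrew before placebo.

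- By treatment received, at least one dose: 3/10 = 30%.
- By assignment: 3/12 = 25%.
- Excluding all three people who lack a period: (3−1)/(10−1) = 2/9 = 22%.

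The exclusion removes the dilution from the two never exposed, but it also removes an insulin event.

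**Placebo side.** In the same case 11 of 12 took placebo, so counting by assignment multiplies the placebo rate by 11/12 = 0.92.

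**The case against.** The strongest reply is that the sentence after the quoted rule may already prevent dilution. A placebo-first participant who leaves before Visit 7 has no insulin-period data. If that counts as missing, the person is excluded and the insulin denominator is the exposed group. This reading is available, so a reader should not infer that the plan does count never-exposed people under insulin; no section states the denominator. The reply does not settle the matter, for two reasons. Someone who leaves early has an adverse event record up to that point, and the absence of an event is normally counted as no event, so it is unclear that the exclusion is triggered. If it is triggered, it can delete insulin events.

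Other parts of the reply stand:

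- A reader might take "We estimate a need to consent up to 20 subjects in order to reach this goal" to mean that heavy loss after randomisation is expected. It does not show that. Consent comes before screening (Sections 5 and 7.1.1), so the gap between 20 and 10 includes screen failures, and Section 7.2 provides separately for withdrawal before Visit 2.
- A reader might infer that the comparison always favours insulin. It does not: insulin-first participants who leave before placebo dilute the placebo rate.
- Other safeguards exist. Relatedness is judged event by event (Section 11.3), the DSMB reviews accumulating safety data (Section 13.2), and non-severe hypoglycaemia is captured through the CGM data instead of as an adverse event (Section 11.6.1).
- The missing rule for washout events is a separate gap, not caused by the intention-to-treat sentence.

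**Conclusion.** The point holds conditionally. Section 12.1 gives two rules that conflict for adverse events in people who miss a period, and either can understate the insulin event rate: the first by enlarging the denominator, the second by removing a person together with an event.

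The dilution is exactly (R−d)/R. It is nil if every randomised participant takes insulin, and 0.92 to 0.75 for one to three never exposed out of 12. These are assumed values, because the documents supply neither R nor d. Participants who complete both periods are unaffected under either rule, so only non-completers matter. The attribution gap for washout and follow-up events exists even with no losses.

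The documents do not support saying that the insulin rate is diluted as a matter of fact, nor that the bias runs in one direction for the insulin–placebo comparison. The primary CGM analysis and its power are outside this point. The consequence is modest, but the change is worth making in a trial whose stated purpose is safety.

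**What to change.** In Sections 12.1 and 12.3:

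1. Limit the intention-to-treat sentence to the primary CGM contrast.
2. State that the missing-data exclusion does not apply to adverse events.
3. Summarise adverse events by treatment actually received. The denominator for each treatment is all participants who took at least one dose of it, whether or not they completed the other period.
4. Show events that start in washout or follow-up on a separate line, by the last treatment taken. This is one convention among several; what matters is that it is fixed beforehand.

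The cost is SAP wording and a first-dose date recorded for each participant and treatment. The accountability logs in Section 13.8 do not list dosing dates, so the case report form should capture them. The first insulin dose is already given in clinic (Sections 7.1.2 and 7.1.7). The placebo start needs the same record. If nobody misses a period, the denominators are unchanged and only the washout and follow-up line is new.
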